5.10 Analysis of Primary Variables

All analyses will be based on the safety population. Subjects with missing information will be excluded from the analyses of the relevant variable.

Primary endpoint

The primary endpoint will be the nature and occurrence of SAEs and AEs including application of sick day rules and adrenal crises observed throughout the study. The main safety analyses are described in section 5.11 below. However, additional investigations may be performed depending on the collected information, such as time to onset of the events, relationship to another medications and/or relationship to other factors.

In any case, a summary of the number and percentage of subjects with an adrenal crises and the number and percentage of subjects with an

implementation of sick day rules and their main reasons will be presented for each cohort and overall by visit and overall.

Secondary endpoints

The secondary endpoint linear Growth Velocity (GV), in terms of cm/year, will be determined for each visit after baseline using the following equation:

$$GV = 12 * (H2 - H1) / D2$$

where H1 is the height/length (in cm) at the baseline visit (visit 1), H2 is the height/length (in cm) at the selected visit and, D2 is the time (in months) between the selected visit and baseline. The Growth Velocity-SDS (linear growth velocity standard deviation score [SDS]) or the so called z-score is then calculated by

$$Z = (GV - \mu) / SD$$

where μ is the mean value and SD the standard deviation of a age and gender matched reference population.

The growth velocity-SDS (GV-SDS) will be derived for each visit after baseline and presented by visit and overall for the safety population.

For the metabolic parameters including cortisol (all subjects) and androgens (17-OHP, A4 and testosterone) in CAH subjects only, at each scheduled time point over the course of the study (at each visit) the following will be displayed by cohort and overall: the number of subjects, mean, standard deviation, median value, and range of values (min, max). In addition, the absolute changes from baseline (last value before intake of Infacort®) will be presented, if appropriate. These summaries will be supported by a graphical presentation of values over time.

Any unscheduled laboratory evaluations will be listed only.

Additional analyses

The number and percentage of subjects for each category of the Tanner Development Stage will be displayed over time for each of the three systems [pubic hair (both sexes), breast (females), genitalia (male)] and for each cohort and overall in the safety population.

Shift tables comparing baseline (visit 1) ratings with the ratings at the interim visits will be presented for each category by cohort and overall.

Tables will be omitted, if not useful.

5.11 Analysis of Safety Variables

These analyses will be conducted for the safety population only and no formal statistical testing will be performed.

Due to the low number of subjects in this study, and depending on the reported events, several of the below mentioned tables may not provide useful information. In this case tables will be omitted.

Adverse Events

For the safety analysis only AEs with onset after the intake of Infacort® (treatment emergent AEs) will be displayed in summary tables. Events which started before intake will be listed only.

AEs will be coded using the MedDRA dictionary (version 18.1 or higher) and will be presented on the MedDRA preferred term level.

An overview summary will show both the number of events and the number of subjects for any AE, intensity (mild, moderate, severe), relationship and seriousness (yes, no).

Treatment emergent AEs will be summarized regardless of severity and relationship. Within each subject, multiple reports of events that map to a common MedDRA term (preferred term) will be condensed into a single AE. The tables will list for each AE the number of events and the number and percentage of subjects in whom the event occurred. AEs will be grouped by system organ class (SOC).

For the summary of treatment emergent AEs by SOC, preferred term, and maximum severity, a subject who experienced more than one episode of a particular coded AE will be counted only once by the maximum severity of these episodes (preferred term). AEs with missing severity will be classified as having the highest severity.

Treatment emergent AEs classified in the CRF as related to the study medication will also be summarised by the classification, SOC and preferred term. Multiple occurrences of the same events with different relatedness will be counted once based on the highest relatedness. AEs with missing relationship will be classified as related to study drug.

All SAEs will be tabulated, if useful and listed separately. All AEs leading to withdrawal will be tabulated, if useful and all withdrawals listed including the reason for premature termination.

Clinical laboratory evaluations

For each laboratory parameter, at each scheduled time point over the course of the study (at each visit), the following will be displayed: the number of subjects, mean, standard deviation, median value, and range of values (min, max). In addition, the absolute changes from baseline (last value before intake of Infacort®) will be presented, if appropriate. For categorical parameters the number and percentage of subjects per category will be presented. Abnormal laboratory values (out of reference range) will be flagged in the listings.

Any unscheduled laboratory evaluations will be listed only.

Vital signs, Weight and Height

For each parameter (systolic blood pressure, diastolic blood pressure, pulse, temperature, weight and height/length, if available) the observed values and

changes from baseline (Visit 0) will be summarised over time by cohort and overall using descriptive statistics. In addition, z-scores based on age and gender matched reference population will be derived for the two variables height and weight and presented by visit.

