### 13.3.2 Statistical Evaluation

#### 13.3.2.1 *Adverse events*

The analysis of AE data will be described in detail in the SAP. All information obtained on AEs will be displayed in listings and subject, including demographic information. The number and percentage of subjects with AEs will be tabulated by System Organ Class (SOC) and Preferred Term (PT). A subject with multiple AEs within a SOC or PT is only counted once towards the total of this SOC or PT.

Further AEs tables, for example by severity, relationship or outcome, will be presented if the number of events make such table useful information.

Analyses and detailed listings of AEs with particular relevance for the formulation (such as choking, vomiting related to dosing etc.) and to AI (sick days, adrenal crisis etc.) will be presented separately.

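### Read literally, SAP 5.11 makes the event count in each preferred-term row of Table 10.2 equal the subject count, so no SAP summary table shows repeat episodes by term

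*SAP*

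**What the plan says.** SAP 5.10 defines the endpoint: "The primary endpoint will be the nature and occurrence of SAEs and AEs including application of sick day rules and adrenal crises". It refers the main analysis to SAP 5.11, which sets the counting rules.

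- **Overview (Table 10.1).** "An overview summary will show both the number of events and the number of subjects for any AE", with breakdowns by intensity, relationship and seriousness. No condensing is mentioned here.
- **Events by SOC and PT (Table 10.2).** Within each subject, "multiple reports of events that map to a common MedDRA term (preferred term) will be condensed into a single AE". The next sentence reads: "The tables will list for each AE the number of events and the number and percentage of subjects in whom the event occurred".
- **Severity (Table 10.4).** A subject with several episodes of one coded AE counts once, at the worst severity.
- **Relatedness (Table 10.3).** "Multiple occurrences of the same events with different relatedness will be counted once based on the highest relatedness".
- **Withdrawals and SAEs (Tables 10.5 and 10.6).** No counting rule is given.

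Protocol 13.3.2.1 tabulates numbers and percentages of subjects by SOC and PT. Its once-only rule is worded for the subject: "A subject with multiple AEs within a SOC or PT is only counted once towards the total of this SOC or PT".

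**The concern.** The protocol's rule is the usual one for a subject count. The SAP's sentence acts on the AE itself and is followed directly by an instruction to tabulate events per AE. A programmer who applies the sentences in the order written collapses the data to one record per child and PT, then counts. The event column then adds nothing to the subject column in any PT row. Another programmer could apply the rule to the subject column only and produce a different Table 10.2 from the same data.

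This bears on the primary endpoint of an open-ended study, and the protocol uses repeat events in several places. Section 11.1 lets the investigator consider withdrawal after repeated unexplained sick-day episodes or crises. Section 12.2 collects AE frequency. Section 12.5 relies on aggregate analyses to show whether anticipated events exceed expectation. Section 12.9.2 names a rise in the rate of an expected serious reaction as possible grounds for expedited reporting. A table meant to show events by PT should be able to show recurrence.

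**Working it through.** The plan states no event rate or expected count, so there is no figure of its own to reproduce. The check has two parts.

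**1. What the rule does to counts**

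Under the literal reading:
- events in a PT row = number of distinct children with that PT = the subject count of that row;
- events summed over PTs = number of distinct child-PT pairs, which can exceed the number of children.

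A made-up example with three children:

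| Child | Pyrexia | Vomiting | Gastroenteritis |
|---|---|---|---|
| 1 | 5 | 3 | 0 |
| 2 | 1 | 0 | 0 |
| 3 | 0 | 2 | 2 |

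| | Pyrexia | Vomiting | Gastroenteritis | Total |
|---|---|---|---|---|
| All episodes | 6 | 5 | 2 | 13 |
| After condensing | 2 | 2 | 1 | 5 |
| Children | 2 | 2 | 1 | 3 |

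Each PT row has events equal to children. The total does not: 5 condensed events in 3 children. An uncondensed Table 10.1 would report 13 events, while the PT rows of Table 10.2 would sum to 5.

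The same holds within one SOC. If one child has 3 episodes of vomiting and 2 of diarrhoea, and a second child has 1 of vomiting, then 6 episodes become 3 condensed events in 2 children.

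**2. How much is lost for one PT**

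Inputs: N = 24, the maximum number of subjects (SAP section 4; Protocol 13.4). The mean number m of episodes of that PT per child over the whole follow-up is an assumption, taken as Poisson and the same for every child.

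- All episodes = N × m
- Expected condensed events = N × (1 − e^(−m))
- Share lost = 1 − (1 − e^(−m)) / m

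| m (assumed) | All episodes | Condensed events | Share lost |
|---|---|---|---|
| 0.25 | 24 × 0.25 = 6 | 24 × 0.221 = 5.3 | 12% |
| 0.5 | 24 × 0.5 = 12 | 24 × 0.393 = 9.4 | 21% |
| 1 | 24 × 1 = 24 | 24 × 0.632 = 15.2 | 37% |
| 2 | 24 × 2 = 48 | 24 × 0.865 = 20.8 | 57% |
| 4 | 24 × 4 = 96 | 24 × 0.982 = 23.6 | 75% |

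The share lost depends on m, not on N. It is modest for rare terms and large for terms that recur.

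**The case against.** The best answer is that the SAP does not say condensing precedes the event count. It asks for events and subjects as two quantities, which makes sense only if they can differ. On that view the rule was meant for the subject column, as in the protocol. This stands as a possible intention, so the literal reading is not the only one. But no sentence limits the rule to subjects or says that the event column counts all episodes. Where SAP 5.11 does want a subject-level rule, for maximum severity, it names the subject as the thing counted once.

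A reader might also infer more than the documents support:

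- **That recurrent harm disappears from the report.** It does not. Table 10.1 shows events separately from subjects, every AE and SAE is listed (SAP Appendix 7), and with at most 24 children the listings can be read child by child. Protocol 13.3.2.1 and 13.3.6 add separate analyses and listings of formulation- and AI-related events and sick-day frequency tables. These safeguards have limits. Table 10.1 is not by PT, the SAP's crisis and sick-day summaries in 5.10 count subjects, and tables may be omitted if judged not useful.
- **That all of Tables 10.2 to 10.6 are affected.** The condensing sentence belongs to the summary regardless of severity and relationship, which is Table 10.2. Tables 10.3 and 10.4 have their own once-only rules, which are reasonable. Tables 10.5 and 10.6 have none, so saying that several serious episodes would show as one assumes the Table 10.2 rule carries over.
- **That events equal children throughout.** This holds for PT rows only, not for SOC or overall totals.
- **That the undercount is several-fold.** That needs high assumed rates. The two years in Protocol section 8 is the expected time from study initiation to authorisation, not follow-up per child. Nor do the documents show that nearly every child will have each common event.

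**Conclusion.** The point holds as a moderate defect in a stated counting rule. Applied as written, SAP 5.11 makes events equal subjects in each PT row of Table 10.2, breaks the reconciliation with Table 10.1, and departs from Protocol 13.3.2.1. No SAP summary table would then give episode counts by PT. The illustrated loss from the event column, 12% to 75% for means of 0.25 to 4 episodes per child, rests on an assumed Poisson recurrence and not on any figure in the documents. Unequal rates between children would change it. The study is descriptive, so no test or decision threshold turns on this column, and the individual events remain in the listings. That is why the point is not rated higher.

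**What to change.** Replace the condensing sentence in SAP 5.11 with wording such as:

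> Subjects are counted once per PT and SOC; the number of events counts every reported treatment-emergent episode. Once-only counting applies only to the subject columns and to the maximum-severity and highest-relatedness tables.

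State that the same event-counting rule applies to Tables 10.1, 10.2, 10.5 and 10.6. Add a programming check that the PT event counts in Table 10.2 sum to the event total in Table 10.1.

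The cost is a short change of SAP wording and one check, with no new data. The downside is that reported event counts become larger.

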With proper treatment and compliance, patients with cortisol deficiency can live a normal life span without limitations. However, the prognosis for an untreated patient is poor. Death is a common outcome, usually from hypotension or cardiac arrhythmia secondary to hyperkalaemia, unless replacement steroid therapy is begun. Glucocorticoid replacement in CAH aims both to replace cortisol and prevent ACTH-driven androgen excess (Dauber et al., 2010). This is challenging, since therapy aiming to normalise ACTH and reducing androgen levels results in excess glucocorticoid exposure with associated complications including short stature, obesity, hypertension and an adverse metabolic profile. Striking the balance between too much and too little glucocorticoid treatment is especially difficult as currently available glucocorticoid formulations cannot replicate the circadian rhythm of cortisol secretion and are not formulated for the paediatric population. CAH is a life-long chronic disorder. In childhood, treatment focuses on issues of gender assignment, genital surgery, optimisation of growth and pubertal development. Priorities change with increasing age, focusing on fertility in early adult life and prevention of metabolic syndrome and osteoporosis in middle and older age, respectively.

Other causes for AI besides CAH include congenital adrenal hypoplasia, lipoid adrenal hyperplasia and hypopituitarism – all of which are extremely rare.

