### **Interim Visits:**

- Physical examination
- Height/length
- Weight
- BMI and BSA (derived)
- Vital signs

- Blood pressure (if possible)
- Heart rate
- Temperature
- Concomitant medication
- SAEs and AEs, including application of sick day rules and adrenal crises
- Dried blood spot sampling (cortisol [all subjects], and 17-OHP, A4, testosterone [CAH subjects only]) every 6 months following the first 2 months of treatment, unless required after 3 months. Where possible the blood spot sample should be taken in the morning. The time of blood sampling and the time of the last glucocorticoid dose will be recorded.
- Blood sampling (electrolytes, renin, haematocrit, and any additional cortisol data) where taken as part of routine clinical care (normally once a year). The time of blood sampling and the time of the last glucocorticoid dose will be recorded.
- Tanner development stage
- Dose of Infacort®
- Problems associated with administration/dosing

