7.1 Demographic and Baseline Characteristics

Table 1.1	Subject disposition – Screening population
Table 1.2	Reasons for study discontinuation – Safety population
Table 1.3	Protocol deviations – Safety population
Figure 1	Subject disposition – Screening population
Table 2.1	Gender, ethnicity, ethnic origin, age [days] and causes of adrenal insufficiency – Safety population
Table 2.2	Height, weight, body mass index, body surface area – Safety population
Table 3.1	Past medical conditions (MedDRA system organ classes) – Safety population
Table 3.2	Concurrent medical conditions (MedDRA system organ classes) – Safety population
Table 4.1	Physical examination over time – Safety population
Table 4.2	Physical examination change from baseline – Safety population
Table 5.1	Concomitant medications at baseline at ATC levels 1 and 2 – Safety population
Table 5.2	Concomitant medications started after baseline at ATC levels 1 and 2 – Safety population
Table 6.1	Extent of Exposure – Safety population
Table 6.2	Administration problems, less than 75% intake – Safety population
Table 6.3	Administration problems, more than the prescribed dose – Safety population
Table 6.4	Number of days with a correct intake of Infacort [®] - Safety population

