7.3 Safety Results

Table 10.1	Overview of all adverse events – Safety population
Table 10.2	Subjects with adverse events, preferred term grouped by MedDRA system organ class – Safety population
Table 10.3	Relationship of adverse events, preferred term grouped by MedDRA system organ class – Safety population
Table 10.4	Severity of adverse events, preferred term grouped by MedDRA system organ class – Safety population
Table 10.5	Adverse events leading to withdrawal, preferred term grouped by MedDRA system organ class – Safety population

Table 10.6	Serious adverse events, preferred term grouped by MedDRA system organ class – Safety population
Table 11.1	Descriptive statistics of routine laboratory values – Safety population
Table 11.1.1	Change from baseline of routine laboratory values – Safety population
Table 12.1	Time course of systolic/diastolic blood pressure [mmHg], pulse [bpm], temperature [°C], weight [kg] and height[cm] – Safety population
Table 12.1.1	Change from baseline in systolic/diastolic blood pressure [mmHg], pulse [bpm], temperature [°C], weight [kg] and height [cm] – Safety population
Table 12.2	Z-scores for weight and height – Safety population

Subject Data Listings

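### Blood pressure in growing children is summarised only as raw values and raw change, so a modest adverse trend cannot be reliably told from growth; a narrower gap is that BMI is not scored over time

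*SAP*

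**What the plan says.** Protocol 5.1, writing about treatment of CAH, says that treating to normalise ACTH and lower androgens leads to "excess glucocorticoid exposure with associated complications including short stature, obesity, hypertension and an adverse metabolic profile". The primary objective (protocol 6.1) is long-term safety, and the synopsis lists vital signs among the safety assessments.

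SAP 5.11 covers systolic and diastolic pressure, pulse, temperature, weight and height in one paragraph. Observed values and "changes from baseline (Visit 0) will be summarised over time by cohort and overall using descriptive statistics" (Tables 12.1 and 12.1.1). Standardisation is added for body size only: "z-scores based on age and gender matched reference population will be derived for the two variables height and weight and presented by visit". The matching output is Table 12.2, "Z-scores for weight and height – Safety population".

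Protocol 8.1 derives BMI at the initial, interim and final visits. In the SAP, BMI is defined in 5.4 with the baseline characteristics, and its only named table is Table 2.2 in section 7.1, "Height, weight, body mass index, body surface area". SAP 5.1 has a general rule that derived variables are presented by visit where appropriate, which could yield raw BMI over time. Neither document plans a BMI score or a blood pressure score.

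Protocol 13.3.7 says that abnormal or clinically significant vital signs will be flagged, on condition that ranges are available. The vital signs paragraph of SAP 5.11 does not repeat this; the SAP specifies out-of-range flags for laboratory values only.

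**The concern.** Blood pressure and BMI both change with age in healthy children. The study has one arm, so no concurrent group shows what development alone would do. Summaries are organised by study visit, by cohort and overall, not by attained age. A mean raw change in blood pressure is therefore the sum of development and any effect of treatment, and nothing in the planned tables separates the two. The error can go either way: ordinary growth may be read as a rise, or a modest real rise may be put down to growth.

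The plan already accepts age- and gender-matched scoring for height and weight. The same logic is not applied to blood pressure, nor to weight relative to height, although hypertension and obesity stand beside short stature in the protocol's own list of complications.

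**Working it through.** **1. Named complication against planned summary**

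| Complication (protocol 5.1) | Planned summary over time | Referenced to age and sex? |
|---|---|---|
| Short stature | Height z-score by visit (SAP 5.11, Table 12.2) | Yes |
| Obesity | Weight z-score by visit (Table 12.2); BMI has a named table at baseline only (Table 2.2) | Weight yes, BMI no |
| Hypertension | Raw values and raw change (Tables 12.1, 12.1.1) | No |

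The plan states no figure on this point, so there is none to reproduce. The arithmetic below illustrates size only.

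**2. Blood pressure**

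From the documents: at most 24 children (protocol 13.4); under 6 years at entry to the parent study (protocol 9.3), including a neonatal cohort (protocol Appendix 6); marketing authorisation expected within 2 years of study start (protocol 8), taken here as T = 2. Individual follow-up may be shorter or longer. Assumed: normal drift d = 1 to 3 mmHg a year; SD of change 8 to 12 mmHg.

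- Mean raw change with no harm = d × T: 1 × 2 = 2 to 3 × 2 = 6 mmHg.
- 95% half-width of a mean = 1.96 × SD / √24: 1.96 × 8 / 4.90 = 3.2 to 1.96 × 12 / 4.90 = 4.8 mmHg. It is wider if readings are missing.
- Drift relative to half-width: 2 / 4.8 = 0.4 to 6 / 3.2 = 1.9.

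An observed mean of +4 mmHg at 2 years fits a drift of 2 mmHg a year and no effect (2 × 2 + 0). It fits equally well a drift of 1 mmHg a year and an adverse effect of 2 mmHg (1 × 2 + 2). The raw summary cannot choose between them.

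For infants, assume a first-year rise of 10 to 25 mmHg, 8 children and an SD of 10. The SE is 10 / √8 = 3.5, so growth alone is 10 / 3.5 = 2.8 to 25 / 3.5 = 7.1 SE. This applies to the first year of life only. At 1 to 3 mmHg a year, the same 8 children would show 2 / 3.5 = 0.6 to 6 / 3.5 = 1.7 SE over 2 years.

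**3. BMI**

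Since log BMI = log W − 2 log H, the change in BMI SDS is approximately (ΔW × s_W − 2 × ΔH × s_H) / s_B. Here ΔW and ΔH are changes in weight and height SDS, and s_B = √(s_W² + 4 s_H² − 4 ρ s_W s_H). The SDs of log weight (s_W) and log height (s_H) and their correlation ρ are assumptions.

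| s_W | s_H | ρ | ΔW = 0, ΔH = −0.5 | ΔW = +0.5, ΔH = −0.5 |
|---|---|---|---|---|
| 0.11 | 0.040 | 0.7 | +0.51 | +1.21 |
| 0.13 | 0.045 | 0.7 | +0.48 | +1.18 |
| 0.12 | 0.040 | 0.6 | +0.42 | +1.04 |
| 0.12 | 0.040 | 0.8 | +0.54 | +1.36 |

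A mean shift of this kind can be partly worked out from the two columns of Table 12.2. The number of affected children cannot. Suppose weight and height scores each have mean 0 and SD 1, with s_W = 0.12, s_H = 0.04 and ρ = 0.7 in the reference. By simulation, the share of children with BMI SDS above 2 is 0.2%, 2.3%, 6.7% or 11.7% when the within-child correlation of the two scores is 0.9, 0.7, 0.4 or 0. The separate group summaries would be identical in all four cases.

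**The case against.** Several points on the other side are sound.

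- Weight as well as height is scored by visit, and weight SDS is a protocol secondary endpoint. Normal weight gain will not by itself look like harm. With at most 24 children and all data listed, a reader can see a falling height with a steady weight child by child. This stands, and it is why the BMI gap is the smaller one.
- A reader might infer that obesity and hypertension cannot be assessed at all. The documents do not support that. The primary endpoint is adverse events, which protocol 12 allows to be detected through examination and vital signs, and protocol 8.6 requires significant examination findings that meet the definition to be recorded. What remains is that protocol 12.1 counts abnormal test results only if they cause symptoms, are clinically significant or need therapy. A slow, symptomless drift may not qualify.
- Protocol 13.3.7 foresees flagging. It does so conditionally, alongside the subject listings, and the SAP omits it.
- Protocol 5.1 is background, not a list of endpoints. The children receive their usual clinically appropriate hydrocortisone dose in a new formulation, and without a control arm a score would still not isolate a formulation effect. True, but a score does remove the expected age trend, which is the part that can be removed.
- The blood pressure remedy is weakest where drift is largest: readings are taken only if possible (protocol 8.12.1), and a reference may not reach infants. Protocol Appendix 7 records that growth velocity was dropped because reference values were lacking. This limits the remedy but does not remove the case for it at older ages.
- IDMC reviews follow a separate SAP that is not available here, so what it plans for blood pressure is unknown.

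**Conclusion.** The point holds as a limited weakness in the safety summaries. For blood pressure, a modest adverse trend cannot be reliably told from growth in the planned tables: growth alone would give about +2 to +6 mmHg over 2 years, against a half-width of 3.2 to 4.8 mmHg in 24 children, and more in infants. For body size the gap is narrower: a change of roughly +0.4 to +0.5 BMI SDS can accompany an unchanged weight SDS and a height SDS down by 0.5, and no planned score shows this within the child.

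Drift rates, SDs, correlations and the group of 8 infants are assumptions; only the sample size, age range and expected 2 years come from the documents. Two stronger readings should not be drawn. Normal growth can, but need not, appear as harm, since at 1 to 3 mmHg a year the drift may lie within the noise. The multiple-SE figure for infants should not be carried over to the whole study.

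**What to change.** In SAP 5.11 and Table 12.2, add BMI SDS by visit, or weight-for-length SDS in infants, from the heights and weights already recorded. Name the reference.

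Alongside the raw blood pressure summaries, add age- and sex-referenced scores or percentiles, height-referenced where the source allows. Report the number of children above a prespecified percentile, with the number measured as denominator. Restrict this to ages that a named reference covers, and show raw values by attained age elsewhere. Carry the vital signs flag of protocol 13.3.7 into the SAP and name the ranges it will use.

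The cost is SAP wording, derivations and a few table columns, with no new measurement. The downside is that a blood pressure reference has to be chosen, it may not cover neonates and infants, and readings taken only where possible will leave gaps.
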